7.5 Co-Enrollment on Additional Studies

Patients enrolled on this study will be approached for co-enrollment on PA15-0315 prospective study to assess immune-related adverse events when receiving immunotherapy at the University of Texas MD Anderson Cancer Center ([name]). All samples and scans will be collected using procedures characterized in this protocol, and all patients will be consented for procedures done under this protocol separately.

Patients enrolled on this study will be approached for co-enrollment on the 2014-0938, APOLLO (Adaptive Patient-Oriented Longitudinal Learning and Optimization)

protocol, which is an MD Anderson Moon Shot platform. All samples will be collected using procedures characterized in this protocol, and all patients will be consented for procedures done under this protocol separately.

8.0 ADVERSE EVENT REPORTING

8.1 Adverse Events

All observed or volunteered AEs regardless of treatment group or suspected causal relationship to the investigational product(s) will be reported as described in the following sections.

For all AEs, the investigator must pursue and obtain information adequate both to determine the outcome of the AE and to assess whether it meets the criteria for classification as a serious adverse event (SAE) requiring immediate notification to Pfizer or its designated representative. For all AEs, sufficient information should be obtained by the investigator to determine the causality of the AE. The investigator is required to assess causality. Follow-up by the investigator may be required until the event or its sequelae resolve or stabilize at a level acceptable to the investigator, and the MDACC IND Office concurs with that assessment.

As part of ongoing safety reviews conducted by the MDACC IND Office, any non-serious AE that is determined by the MDACC IND Office to be serious will be reported by the MDACC IRB as an SAE per MDACC institutional policy. To assist in the determination of case seriousness further information may be requested from the investigator to provide clarity and understanding of the event in the context of the clinical study.

The active reporting period begins from the time that the patient provides informed consent through 30 calendar days after the last administration of the investigational product.

8.2 Definition of Adverse Event

An adverse event is defined in the International Conference on Harmonization (ICH) Guideline for Good Clinical Practice as “any untoward medical occurrence in a patient or clinical investigation subject administered a pharmaceutical product and that does not necessarily have a causal relationship with this treatment” (ICH E6:1.2).

An adverse event can therefore be any unfavorable and unintended sign (including an abnormal laboratory finding, for example), symptom or disease temporally associated with the use of a medicinal product, whether or not it is considered related to the medicinal product.

8.3 Definition of Serious Adverse Event (SAE)

An adverse event or suspected adverse reaction is considered “serious” if, in the view of either the investigator or the sponsor, it results in any of the following outcomes:

- Death
- A life-threatening adverse drug experience – any adverse experience that places the patient, in the view of the initial reporter, at immediate risk of death from the adverse experience as it occurred. It does not include an adverse experience that, had it occurred in a more severe form, might have caused death.
- Inpatient hospitalization or prolongation of existing hospitalization
- A persistent or significant incapacity or substantial disruption of the ability to conduct normal life functions.
- A congenital anomaly/birth defect.

Important medical events that may not result in death, be life-threatening, or require hospitalization may be considered a serious adverse drug experience when, based upon appropriate medical judgment, they may jeopardize the patient or subject and may require medical or surgical intervention to prevent one of the outcomes listed in this definition. Examples of such medical events include allergic bronchospasm requiring intensive treatment in an emergency room or at home, blood dyscrasias or convulsions that do not result in inpatient hospitalization, or the development of drug dependency or drug abuse (21 CFR 312.32).

- **Important medical events as defined above, may also be considered serious adverse events. Any important medical event can and should be reported as an SAE if deemed appropriate by the Principal Investigator or the IND Sponsor, IND Office.**

- All events occurring during the conduct of a protocol and meeting the definition of a SAE must be reported to the IRB in accordance with the timeframes and procedures outlined in "The University of Texas M. D. Anderson Cancer Center Institutional Review Board Policy for Investigators on Reporting Unanticipated Adverse Events for Drugs and Devices". Unless stated otherwise in the protocol, all SAEs, expected or unexpected, must be reported to the IND Office, regardless of attribution (within 5 working days of knowledge of the event).
- **All life-threatening or fatal events**, that are unexpected, and related to the study drug, must have a written report submitted within **24 hours** (next working day) of knowledge of the event to the Safety Project Manager in the IND Office.
- **Unless otherwise noted, the electronic SAE application (eSAE) will be utilized for safety reporting to the IND Office and MDACC IRB.**
- **Serious adverse events will be captured from the time of the first protocol-specific intervention, until 30 days after the last dose of drug, unless the participant withdraws consent. Serious adverse events must be followed until clinical recovery is complete and laboratory tests have returned to baseline, progression of the event has stabilized, or there has been acceptable resolution of the event.**
- **Additionally, any serious adverse events that occur after the 30 day time period that are related to the study treatment must be reported to the IND Office. This may include the development of a secondary malignancy.**

8.4 Reporting to FDA

Serious adverse events will be forwarded to FDA by the IND Sponsor (Safety Project Manager IND Office) according to 21 CFR 312.32.

It is the responsibility of the PI and the research team to ensure serious adverse events are reported according to the Code of Federal Regulations, Good Clinical Practices, the protocol guidelines, the sponsor's guidelines, and Institutional Review Board policy.

8.5 Investigator Communications with Pfizer

For SAEs, the active reporting period to Pfizer or its designated representative begins from the time that the patient provides informed consent through 30 calendar days after the last administration of the investigational product. SAEs occurring to a patient after the active reporting period has ended should be reported to Pfizer if the investigator becomes aware of them; at a minimum, all SAEs that the investigator believes have at least a reasonable possibility of being related to investigational product are to be reported to Pfizer.

AEs (serious and non-serious) should be recorded on the case report form (CRF) from the time the patient has taken at least one dose of investigational product through the patient's last visit.

If a patient begins a new anticancer therapy, the AE reporting period for non-serious AEs ends at the time the new treatment is started. Death must be reported if it occurs during the SAE reporting period after the last dose of investigational product, irrespective of any intervening treatment.

The investigator primary responsibilities in the safety reporting are to identify and follow-up on Serious Adverse Events (SAEs) experienced by participants in the study and to forward the information to IRB, IND Office, and Pfizer, as required by local regulations (for regulatory reporting) and Investigator-Initiated Research (IIR) agreement (for reporting to Pfizer).

The following reportable events must be submitted to Pfizer within 24 hours (or immediately for death or life-threatening events) using the MDACC SAE form with the Pfizer Reportable Events Fax Cover Sheet with each SAE submission.

- Serious Adverse Events
- Exposure during Pregnancy or Breastfeeding (even if not associated with an adverse event)
- Occupational exposure (even if not associated with an adverse event)

- Potential drug-induced liver injury (Hy's Law cases): These events are considered important medical events and should be reported as SAEs.

Contact information for submission of reportable events to Pfizer:

- **Fax: Pfizer U.S. Clinical Trial Department, [contact].**

Or

- **E-mail: [contact] , specifying:**
PROTOCOL:
SUBJECT:
SITE/PI:
SAE/ONSET:

The MDACC SAE form will be submitted to Pfizer. The following detailed information must be recorded for each serious adverse event in the SAE report form:

- A description of the AE in medical terms according to NCI-CTC Version 4.03, not as reported by the subject.
- The severity grade as assessed by the investigator according to the definitions in NCI-CTC Version 4.03.
- The date of becoming serious and the date of becoming known (if different).
- The reason for seriousness.
- The outcome of the SAE at the time of the report.
- Information on administration of the study drug and chemotherapy and any action taken.
- Information on any treatment procedures necessary for the SAE, concomitant medications, relevant lab tests and relevant medical history.

If in any one subject the same SAE occurs on several occasions, then the SAE in question must be documented and assessed anew each time. The investigator is required to submit SAE Follow-up reports until the SAE has resolved or stabilized and all queries have been answered.

8.6 Recording of Adverse Events

The investigator is responsible for ensuring that all adverse events observed by the investigator or reported by subjects are properly recorded in the subjects' medical records and the electronic case report form.

The following adverse event attributes must be assigned by the investigator:

- Adverse event term according to the NCI-CTC criteria Version 4.03;
- Severity grade according to the NCI-CTC criteria Version 4.03;
- Start date and stop date (or date of last assessment);
- Outcome;
- Causality to study drug and chemotherapy (to be assessed as either related or unrelated);
- Any action taken.

Adverse events will be followed until they resolve to baseline or considered stable. It will be left to the investigator's clinical judgment to determine whether an adverse event is related and of sufficient severity to require the subject's removal from treatment or from the study. A subject may also voluntarily withdraw from treatment due to what he or she perceives as an intolerable adverse event. If either of these situations arises, the subject should be strongly encouraged to undergo an end-of-study assessment and be under medical supervision until symptoms cease or the condition becomes stable.

Pre-existing diseases, when worsening during study therapy, have to be considered as adverse events. They can lead to serious adverse events, if they meet the criteria described in [Section 8.3](#).

Intensity of adverse events will be graded using the National Cancer Institute Common Terminology Criteria for Adverse Events (CTCAE), version 4.03. If an adverse event occurs which is not described in the CTCAE version 4.03, the four-point scale below will be used.

- Mild: Discomfort noticed but no disruption of normal daily activity.
- Moderate: Discomfort sufficient to reduce or affect daily activity.
- Severe: Inability to work or perform normal daily activity.
- Life-threatening: Represents an immediate threat to life.

8.6.1 Laboratory Test Abnormalities

Laboratory test results will be recorded on the laboratory results pages of the eCRF. In the event of unexplained abnormal laboratory test values, the tests should be repeated immediately and followed up until they have returned to the normal range and/or an adequate explanation of the abnormality is found.

Laboratory test value abnormalities as such should not be reported on the AE page of the eCRF as adverse events unless they are treatment-emergent and they satisfy one or more of the following conditions for clinical significance:

- 1) Accompanied by clinical symptoms;
- 2) Leading to a change in study medication (e.g. dose modification, interruption or permanent discontinuation);
- 3) Requiring a change in concomitant therapy (e.g. addition of, interruption of, discontinuation of, or any other change in a concomitant medication, therapy or treatment).

Please note: Any laboratory result abnormality fulfilling the criteria for a serious adverse event (SAE) should be reported as such, in addition to being recorded as an adverse event in the eCRF.

8.6.2 Pregnancy

Pregnancy per se is not considered an AE. A medical occurrence observed in the mother or fetus/newborn would be an AE.

Female patients must be instructed to immediately inform the investigator if they become pregnant during the study. The study treatment must immediately be stopped and the patient must be withdrawn from the study. Pregnancies occurring up to 6 months after the completion of the last treatment cycle must also be reported to the

investigator. The investigator must report all pregnancies within 24 hours of knowledge to Pfizer. The investigator should counsel the patient; discuss the risks of continuing the pregnancy and the possible effects on the fetus. The patient should be monitored until the conclusion of the pregnancy.

Pregnancy occurring in the partner of a patient participating in the study should also be reported to the investigator, MDACC IND Office, and Pfizer. The partner should be counseled and followed as described above.

8.6.2 Adverse Drug Reactions with Concomitant Medication

The investigators must be aware that for all concomitant medications the regulations of post-marketing reporting for suspected adverse drug reactions apply, i.e. reporting to the marketing authorization holder or the local regulatory bodies.

9.0 DATA ANALYSIS/ STATISTICAL METHODS

[name] (Department of Biostatistics at MD Anderson) will perform all statistical analyses. Detailed methodology for summary and statistical analyses of the data collected in this trial will be documented below.

9.1 Analysis Sets

1) Safety Analysis Set

The safety analysis set includes all enrolled patients who receive at least one dose of each study medication in the assigned treatment combination. Patients in Arms A and D must receive at least one dose of avelumab and utomilumab each. Patients in Arm B must receive at least one dose of avelumab and PF-04518600 (OX40) each. Patients in Arm C must receive at least one dose of avelumab, utomilumab, and PF-04518600 (OX40) each. Subjects who have not received at least one dose of each study medication in the assigned treatment combination will be replaced.

2) Full Analysis Set

The full analysis set includes all enrolled patients.

3) Per Protocol Analysis Set

All enrolled patients who are eligible, receive study treatment and who either experience DLT during the first 56 days (following Cycle 1 Day 1) of study treatment or complete the 56-day treatment without DLT will be included. Patients who are lost to follow-up due to reasons unrelated to treatment related AEs are not evaluable for DLT.

The per-protocol population will consist of all patients who are compliant with study assessments and who have no major protocol violations that would compromise the assessment of efficacy. Major violations will be determined independently of knowledge of response to therapy. This population will be used for primary inferences concerning efficacy, however, if there are major differences between the results in this population and those obtained in the treated population, this will be taken into consideration in the decision to continue to later phase studies, or in the design of

further studies.

4) Response Analysis Set

All enrolled patients who are eligible, receive study treatment, have baseline assessments and at least 1 on-study tumor assessment will be considered evaluable for response. Patients who are treated and removed from study prior to on-study tumor assessment because of disease progression will be considered evaluable for efficacy and counted as failures.

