Safety Assessments:	
All adverse events (AEs), including immune-related adverse events (irAEs), occurring during the course of the trial and for up to 30 days after the last dose of study medication will be captured, documented and reported. Toxicity will be graded according to National Cancer Institute Common Terminology Criteria for Adverse Events (CTCAE) version 4.03.
 
If multiple toxicities are seen, the presence of DLT shall be based on the most severe toxicity experienced. DLTs are defined as adverse events (AEs) that are related to study events and occur during the first 2 cycles or 8 weeks of treatment. Toxicity must have possible, probable, or definite attribution to the study drugs.

Statistical Considerations:	All enrolled patients are eligible for the analyses of toxicity and compliance. All patients who received at least 1 dose of study medication are eligible for analysis.

SCHEDULE OF ASSESSMENTS FOR ARMS A, B, AND C (NON-RADIATION)

The Schedule of Assessments table provides an overview of the protocol visits and procedures for Arms A-C. Refer to the [Section 7.0- Assessments](#) of the protocol for detailed information on each assessment required for compliance with the protocol. The investigator may schedule visits (unplanned visits) in addition to those listed on the schedule of activities, in order to conduct evaluations or assessments required to protect the wellbeing of the patient.

Assessments	Treatment Period							Post-Treatment	
	Screening	Cycle 1		Cycle 2		Cycle 3 and Beyond		End of Treatment (EOT)	Follow-Up Visits
	<= 28 Days prior to 1 st Dosing of Study Drug	Day 1 (+/- 2 Days)	Day 15 (+/- 2 Days)	Day 1 (+/- 2 Days)	Day 15 (+/- 2 Days)	Day 1 (+/- 2 Days)	Day 15 (+/- 2 Days)	30 Days after Last Dose of Study Drug (+/- 7 Days)	Every 12 Weeks (+/- 7 Days)
Informed Consent ¹	X								
Verify Eligibility Criteria	X	X							
Medical History ²	X								
Tumor History	X								
Serum or Urine Beta- hCG ³	X	X		X		X		X	
Protocol /Safety Evaluation									
Physical Exam and ECOG ⁴	X	X	X	X	X	X	X	X	
Height ⁵	X								
Weight ⁵	X	X	X	X	X	X	X		
Vital Signs ⁵	X	X	X	X	X	X	X	X	X
12-lead ECG ⁶	X	X		X		X			

Assessments	Treatment Period							Post-Treatment	
	Screening	Cycle 1		Cycle 2		Cycle 3 and Beyond		End of Treatment (EOT)	Follow-Up Visits

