15. For patients on the PF-04518600 (OX40) Arms (B and C) who have had prior exposure to anthracyclines, cardiac enzyme monitoring will be performed at screening, Day 1 of every cycle, and End of Treatment. Troponin T and N-terminal of the prohormone brain natriuretic peptide (NT-proBNP) will be evaluated prior to dosing. No need to repeat on Cycle 1 Day 1 (C1D1) if the screening assessment is performed within 2 days prior to that date. Assessments performed on Cycle 2 Day 1 and Day 1 of each subsequent cycle should be performed within 48 hours prior to dosing. Assessments should also be performed when clinically indicated.
16. For MTD Expansion Arms A-C, avelumab will be administered IV every 2 weeks starting on Cycle 1 Day 15 (and then Days 1 and 15 of Cycle 2 and beyond).
17. For Arm A, utomilumab (4-1BB) will be administered IV every 4 weeks starting on Cycle 1 Day 1 (Day 1 of every cycle).
18. For Arm B, PF-04518600 (OX40) will be administered IV every 2 weeks starting on Cycle 1 Day 1 (Days 1 and 15 of every cycle).
19. For Arm C, utomilumab (4-1BB) will be administered IV every 4 weeks starting on Cycle 1 Day 1 (Day 1 of every cycle). PF-04518600 (OX40) will be administered IV every 2 weeks starting on Cycle 1 Day 1 (Days 1 and 15 of every cycle).
20. CT, MRI, or PET-CT Scans will be performed at screening, then every 2 cycles or 8 weeks +/- 7 days for the first year of treatment. Thereafter tumor assessments will be performed every 3 cycles or 12 weeks +/- 7 days during treatment, independent of cycle delays.
21. Tumor markers (if applicable) will be collected at screening, then every 2 cycles or 8 weeks +/- 7 days for the first year of treatment. Thereafter tumor assessments will be performed every 3 cycles or 12 weeks +/- 7 days during treatment, independent of cycle delays.
22. For MTD Expansion Cohorts in Arms A-C, tumor tissue will be obtained pre- treatment (baseline), between Cycle 1 Day 12-15 (prior to study drug dosing), prior to Cycle 3 Day 1 study drug dosing, and at progression (if achieved stable disease \geq 6 months, partial response, or complete remission) provided there is technically biopsiable tumor, and it is safe for patient to undergo biopsy.

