9.6 Safety Analysis

The safety population will consist of all patients who have received any amount of study medication.

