9.6.1 Safety Evaluation

Safety analyses will be conducted using the Safety Population. For the objective of describing the toxicity profile, descriptive statistics will be provided on the grade and type of toxicity by dose level.

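### The safety analysis set is defined three ways: Section 9.1 requires every assigned drug, Section 9.6 any amount, the synopsis all enrolled; the replacement rules do not agree either

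*Combined protocol and SAP*

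**What the plan says.** **Who is in the safety analysis.**

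- Section 9.1, item 1: "The safety analysis set includes all enrolled patients who receive at least one dose of each study medication in the assigned treatment combination". The section then spells this out arm by arm, naming avelumab and utomilumab for Arm D.
- Section 9.6: "The safety population will consist of all patients who have received any amount of study medication". Section 9.6.1 adds: "Safety analyses will be conducted using the Safety Population".
- Synopsis, Statistical Considerations: "All enrolled patients are eligible for the analyses of toxicity and compliance". The next sentence reads: "All patients who received at least 1 dose of study medication are eligible for analysis".

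**Who is replaced.**

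- Section 9.1: "Subjects who have not received at least one dose of each study medication in the assigned treatment combination will be replaced". No condition on the reason is attached.
- Section 3.3 replaces patients who come off study for reasons other than toxicity or progression, up to 4 cycles in de-escalation and 6 in expansion. For the Arm D de-escalation only, it also replaces patients who miss doses in the DLT period for reasons unrelated to study drug.
- Section 6.5 rules out replacement for withdrawals outside the DLT period, which Section 3.4 sets at 56 days from Cycle 1 Day 1.

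**Timing.** Footnote 16 in both Schedules of Assessments: "avelumab will be administered IV every 2 weeks starting on Cycle 1 Day 15". The agonist is given from Cycle 1 Day 1, and in Arm D radiation precedes it.

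**The concern.** Safety and tolerability is a primary endpoint (Section 2.2.1), and its denominator has competing definitions with nothing to say which prevails. Section 9.6 reads as the operative text because Section 9.6.1 applies it, but Section 9.1 is the section that defines the analysis sets.

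The staggered start makes the difference matter. A patient who receives the agonist and stops for toxicity before Day 15 never receives avelumab. That patient is inside the Section 9.6 population, outside the Section 9.1 set, and replaced under Section 9.1. Membership under Section 9.1 can therefore depend on early toxicity, which is what the analysis measures. Leaving the choice open also allows it to be made after the data are seen.

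**Working it through.** The plan gives no figure on this point to reproduce. The check compares the text and then bounds the effect using Table 12.

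**1. Exposure before avelumab.** Days 1 to 14 of the 56-day DLT window precede the first avelumab dose: 14/56 = 25%.

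**2. One patient under each rule.** Take a patient who receives the agonist and stops on, say, Day 10 for related toxicity.

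| Text | Result |
|---|---|
| Section 9.1, item 1 | Outside the safety set; replaced |
| Section 9.6 | Inside the safety population |
| Synopsis | Inside, under both sentences |
| Section 3.3, off-study rule | Replacement condition not met, because the reason is toxicity |
| Section 3.3, DLT definition | A DLT in the de-escalation |

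**3. Replacement windows.** Section 6.5 with Section 3.4 gives 56 days. Section 3.3 gives 4 × 28 = 112 days or 6 × 28 = 168 days. A patient who leaves at Day 80 of expansion for social reasons is replaced under Section 3.3 and not under Section 6.5.

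**4. Effect on a percentage.** Let m of N treated patients fail Section 9.1. The Section 9.6 rate minus the Section 9.1 rate equals (m/N) × (event rate in the m patients − event rate in the rest). It cannot exceed m/N in either direction.

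- *Pooled tables.* Section 9.6.2 displays adverse events, and Sections 9.6.3 and 9.6.4 summarise laboratory values and vital signs, for all patients combined. Table 12 notes 2 replacements in Arm B and 3 in Arm C. With the stated total of 128, m/N = 5/128 = 3.9%. (The row totals sum to 24 + 28 + 32 + 33 + 6 + 7 = 130, which gives 3.8%.)
- *Summary by dose level (Section 9.6.1).* Arm B: 2/16 = 12.5%. Arm C: 3/17 = 17.6%.

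These are outer limits. They need all the replaced patients to have missed a drug and the event to occur in all of one group and none of the other. The lower limit is 0 throughout, because Table 12 gives no reasons.

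**5. How easily the definitions diverge (assumed rates).** If each patient has probability e of stopping before Day 15, the chance of at least one such patient among 14 is 1 − (1 − e)^14: 25% at e = 2%, 51% at 5% and 77% at 10%.

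**6. Arm D lead-in.** Section 9.6.2 starts the treatment-emergent period at the first study medication, and its listing covers treatment-emergent and post-treatment events. If radiation is not study medication, a lead-in event may be neither, unless judged drug-related. A patient who stops during the lead-in is then also outside the Section 9.6 population. Up to 12 + 14 = 26 planned current-schedule patients pass through this period; that is the number exposed to the gap, not an estimate of those affected.

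**The case against.** **The effect is small and mostly unquantified.** AE tables are pooled, no AE hypothesis test is planned, and nothing ties the five replacements to Section 9.1. Section 3.3 offers another route to replacement in expansion. Table 12 keeps the replaced patients in its totals (Arm B 12 + 16 = 28; Arm C 4 + 11 + 17 = 32). All of this stands. A reader might infer swings of 12.5 or 17.6 points in the main AE tables; the documents do not support that.

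**The Section 9.1 replacement sentence may be an extra trigger rather than a contradiction.** Section 3.3 says when patients are replaced, not that they are replaced in those cases alone, and its missed-dose rule is confined to the Arm D de-escalation. This also stands: Sections 9.1 and 3.3 are in tension, and the direct conflict is between Sections 3.3 and 6.5.

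**Early DLTs are not shown to be lost.** A reader might infer that replaced patients drop out of the DLT count and so distort de-escalation or the 33% stopping rule. Section 3.5 considers all enrolled participants in the DLT analysis, and Section 9.1, item 3, includes patients who "experience DLT during the first 56 days (following Cycle 1 Day 1) of study treatment". What remains is that Section 3.3 calls some replaced patients not evaluable for DLT, which does not match Section 3.5.

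**Radiation is arguably not study medication.** Section 9.1 lists only the two drugs for Arm D, and Section 3.2.4 treats radiation separately from study drug, although Section 5.4.7.4 calls it part of the study treatment regimen. Lead-in events are collected in any case (Arm D Schedule of Assessments; Section 7.1.2). The point is a secondary gap in how those events are classified.

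**Conclusion.** The conflict is real on the current text and should be fixed. Section 9.1 defines a narrower safety set than Section 9.6 and the synopsis, and with the Day 15 avelumab start the narrower set can exclude patients because of early toxicity.

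The consequence is confined to descriptive percentages. For the replacements on record it is 0 to 3.9% of patients in the pooled tables, and at most 2 of 16 (Arm B) or 3 of 17 (Arm C) in the summary by dose level. These bounds take the planned total of 128 as denominator and count only the five replacements noted in Table 12; any other patient who missed a drug would add to them. The direction is unknown. The documents do not show that any DLT is lost or any dose decision changes, so this falls short of a must-fix.

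**What to change.** - Delete the every-drug definition from Section 9.1. Use one safety population in the synopsis, Section 9.1 and Section 9.6: all patients who received any study drug or, in Arm D, any radiation fraction.
- State that replaced patients stay in all safety tables.
- Make the treatment-emergent definition in Section 9.6.2 say how Arm D lead-in events are classified and listed.
- Reconcile the replacement and DLT-evaluability text in Sections 3.3, 3.5, 6.5 and 9.1. Which rule is adopted is for the sponsor and investigator; this review does not choose one.
- Report the number of replacements by arm with reasons, including the five in Table 12.

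The cost is a wording amendment to the synopsis and those sections, with no new patients or assessments. The reasons for the five replacements should already be on file, since the IND Office approved them.
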